5.6.2 Definition of a Serious Adverse Event

A serious adverse event is any untoward medical occurrence that, at any dose:

- a. Results in death
- b. Is life-threatening

NOTE: The term 'life-threatening' in the definition of 'serious' refers to an event in which the subject was at risk of death at the time of the event. It does not refer to an event, which hypothetically might have caused death, if it were more severe.

c. Requires hospitalization or prolongation of existing hospitalization

NOTE: In general, hospitalization signifies that the subject has been detained (usually involving at least an overnight stay) at the hospital or emergency ward for observation and/or treatment that would not have been appropriate in the physician's office or outpatient setting. Complications that occur during hospitalization are AEs. If a complication prolongs hospitalization or fulfills any other serious criteria, the event is serious. When in doubt as to whether "hospitalization" occurred or was necessary, the AE should be considered serious.

Hospitalization for elective treatment of a pre-existing condition that did not worsen from baseline is not considered an AE

d. Results in disability/incapacity, or

NOTE: The term disability means a substantial disruption of a person's ability to conduct normal life functions. This definition is not intended to include experiences of relatively minor medical significance such as uncomplicated headache, nausea, vomiting, diarrhea, influenza, and accidental trauma (e.g. sprained ankle) which may interfere or prevent everyday life functions but do not constitute a substantial disruption

- e. Is a congenital anomaly/birth defect
- f. Medical or scientific judgement should be exercised in deciding whether reporting is appropriate in other situations, such as important medical events that may not be immediately life-threatening or result in death or hospitalization but may jeopardize the subject or may require medical or surgical intervention to prevent one of the other outcomes listed in the above definition. These should also be considered serious. Examples of such events are invasive or malignant cancers, intensive treatment in an emergency room or at home for allergic bronchospasm, blood dyscrasias or convulsions that do not result in hospitalisation, or development of drug dependency or drug abuse
- g. All events of possible drug-induced liver injury (see Section 5.6.5) with hyperbilirubinaemia defined as ALT ≥ 3xULN and bilirubin ≥ 2xULN (>35% direct) (or ALT ≥ 3xULN and INR>1.5, termed 'Hy's Law' events (the INR threshold value stated will not apply to patients receiving anticoagulants)

Laboratory and Other Safety Assessment Abnormalities Reported as AEs and SAEs

Any abnormal laboratory test results (hematology, clinical chemistry, or urinalysis) or other safety assessments (e.g., ECGs, radiological scans, vital signs measurements), including those that worsen from baseline, and felt to be clinically significant in the medical and scientific judgement of the investigator are to be recorded as AEs or SAEs. However, any clinically significant safety assessments that are associated with the underlying disease, unless judged by the investigator to be more severe than expected for the subject's condition, are **not** to be reported as AEs or SAEs.

Pregnancy

Any pregnancy that occurs during study participation must be reported to GSK. To ensure subject safety, each pregnancy must be reported within 2 weeks of learning of its occurrence. The pregnancy must be followed up to determine outcome (including premature termination) and status of mother and child. Pregnancy complications and elective terminations for medical reasons must be reported as an AE or SAE. Spontaneous abortions must be reported as an SAE.

Any SAE occurring in association with a pregnancy, brought to the investigator's attention after the subject has completed the study and considered by the investigator as possibly related to the study treatment, must be reported to GSK within 24 hours of learning of its occurrence.

The National Cancer Institute Common Toxicity Criteria Scale will be used to define grades (severity) of adverse events and toxicities. An adverse event is any untoward medical occurrence in a participant who received study drug, regardless of its relationship to the study drug. Toxicity is an adverse event with a direct relationship to the study drug. All toxicities are adverse events, but not all adverse events are toxicities. This is a determination made by the study investigator. The study investigators will classify adverse events as "definitely or most likely," "possibly," or "very unlikely" due to the study drug. Toxicity will be defined as an adverse event that is definitely, most likely, or possibly caused by the study drug.

The severity of adverse changes in physical signs or symptoms will be classified as follows:

- Grade 1 (Mild): asymptomatic or mild symptoms; clinical or diagnostic observation only; intervention not indicated.
- Grade 2 (Moderate): minimal, local or noninvasive intervention indicated; limiting ageappreciate instrumental ADL (Activities of Daily Living).
- Grade 3 (Severe): medically significant but not immediately life-threatening; hospitalization or prolongation of hospitalization indicated; disabling; limiting self care ADL.
- Grade 4 (Life-threatening): consequences; urgent intervention indicated.
- Grade 5 (Death): event is a direct cause of death.

Assuring patient safety is an essential component of this protocol. The contact PI has primary responsibility for the oversight of the data and safety monitoring. The study investigators will evaluate all adverse events. All subjects who have adverse events, whether considered associated with the use of the study medication or not, must be monitored to determine the outcome.

All untoward medical occurrences observed in subjects will be recorded on the participants' adverse event CRF by the study coordinator under the supervision of a PI, with a particular focus on infections (including location and organism), metabolic or hemodynamic perturbations (e.g., hyperglycemia, hypotension, etc.), liver function test abnormalities, and other, less frequent complications (e.g., neurologic and psychiatric symptoms), as well as having provision for free text entries. Recording all adverse events in pre-specified checklists (and free text entries), will guard against unintended bias. The CRFs will then be reviewed for completeness and internal

consistency.

The clinical course of the adverse event will be followed up according to accepted standards of medical practice, even after the end of the period of observation, until a satisfactory explanation is found or the PI considers it medically justifiable to terminate follow-up.

The PIs will work with the coordinator(s) to prepare a detailed written summary of serious, unexpected, and treatment related adverse events, and will compare, and contrast the event with prior events. The detailed written summary will be provided to the DSMB, IRB, and sponsor.

In addition, the DSMB Report addressing the following information will be submitted to the IRB at the time of continuing review annually or more often as required.

5.6.3 Adverse Events Reporting Timeline

The investigators or site staff are responsible for detecting, documenting and reporting events that meet the definition of an AE or SAE. AEs will be collected from the start of study treatment and until the follow up contact. SAEs will be collected over the same time period as stated above for AEs. However, any SAEs assessed **as related** to study participation (e.g., study treatment, protocol-mandated procedures, invasive tests, or change in existing therapy) or related to a GSK concomitant medication, will be recorded from the time a subject consents to participate in the study up to and including any follow up contact.

The investigators will report life-threatening or fatal unexpected adverse events associated with the use of the study drug or procedures to the DSMB, and the IRB within 24 hours of discovery of the incident with subsequent follow-up submission of a detailed written report.

All SAE will be reported via email notification within 24 hours of awareness to the following sponsor (GSK) contacts including:

- 1) ISS Chairperson
- 2) ISS Managing Director
- 3) GMAL or designee
- 4) LOC Physician
- 5) LOC Safety Contact
- 6) LOC Study Accountable Person
- 7) GCSP Safety Physician
- 8) GCSP Safety Scientist
- 9) [contact]

Serious (but not fatal or life-threatening) and unexpected adverse events associated with the use of the study drugs or procedures must be reported to the DSMB and the IRB within 5 working days with subsequent follow-up submission of a detailed written report.

Adverse Events of Special Interest:

The following adverse events of special interest will be assessed for frequency in the data analyses and final report.

- Serious Hypersensitivity or Infusion Reactions
- Serious infections, including herpes zoster and opportunistic infections
- Malignancy
- Suicidal thought, intent or behaviour

5.6.4 Stopping Rules:

Individual subject-specific stopping rules: A study participant will be discontinued from further study drug treatment/Intervention(s) administration if any of the following occur:

Any clinical adverse event, laboratory abnormality, intercurrent illness, other medical condition or situation occurs such that continued participation in the study would not be in the best interest of the participant.

An unexpected fatal or life-threatening adverse event, which requires discontinuation of study treatment.

Patients who develop acute exacerbations that require an addition to their lung medications, or a hospitalization, will be terminated from the study. Any subject who develops new conditions or statuses that would have been an exclusion criterion, will be terminated from the trial.

Request by the subject to withdraw from the study.

Specific Liver Chemistry Stopping Criteria:

Liver chemistry stopping and increased monitoring criteria have been designed to assure subject safety and evaluate liver event etiology (in alignment with the FDA premarketing clinical liver safety guidance).

- ALT Absolute: $ALT \ge 8x$ upper limit of normal (ULN)
- ALT Increase:
 - \circ ALT \geq 5xULN but <8xULN persists for \geq 2 weeks
 - ALT \ge 3xULN but <5xULN persists for \ge 4 weeks
- Bilirubin: ALT \ge 3xULN and bilirubin \ge 2xULN (>35% direct bilirubin)

All events of ALT \ge 3xULN and bilirubin \ge 2xULN (>35% direct bilirubin) or ALT \ge 3xULN and INR>1.5, if INR measured which may indicate severe liver injury (possible 'Hy's Law'), must be reported as an SAE (excluding studies of hepatic impairment or cirrhosis); INR measurement is not required and the threshold value stated will not apply to subjects receiving anticoagulants.

- INR: ALT \geq 3xULN and INR>1.5, if INR measured
- Cannot Monitor:
 - \circ \quad ALT \geq 5xULN but <8xULN and labs cannot be monitored weekly for $\geq\!\!2$ weeks

- ALT ≥ 3xULN but <5xULN and labs cannot be monitored weekly for ≥4 weeks
- Symptomatic: ALT ≥ 3xULN associated with symptoms (new or worsening) believed to be related to liver injury or hypersensitivity
 - New or worsening symptoms believed to be related to liver injury (such as fatigue, nausea, vomiting, right upper quadrant pain or tenderness, or jaundice) or believed to be related to hypersensitivity (such as fever, rash or eosinophilia)

Required Actions, Monitoring, and Follow up Assessments following ANY Liver Stopping Event Actions:

The study treatment will be Immediately discontinued

The event will be reported to GSK within 24 hours

Liver event follow up assessments will be performed (as stated below)

The subject will be monitored until liver chemistries resolve, stabilize, or return to within baseline (see MONITORING below)

Treatment will not be restarted or rechallenged in the subject

Monitoring:

For bilirubin or INR criteria:

Repeat liver chemistries (include ALT, AST, alkaline phosphatase, bilirubin) and perform liver event follow up assessments within 24 hrs

Monitor subjects twice weekly until liver chemistries resolve, stabilize or return to within baseline

A specialist or hepatology consultation is recommended

For All other criteria:

Repeat liver chemistries (include ALT, AST, alkaline phosphatase, bilirubin) and perform liver event follow up assessments within 24-72 hrs

Monitor subjects weekly until liver chemistries resolve, stabilize or return to within baseline

Follow Up Assessments:

Viral hepatitis serology (Includes: Hepatitis A IgM antibody; Hepatitis B surface antigen and Hepatitis B Core Antibody (IgM); Hepatitis C RNA; Cytomegalovirus IgM antibody; Epstein-Barr viral capsid antigen IgM antibody (or if unavailable, obtain heterophile antibody or monospot testing); Hepatitis E IgM antibody)

Serum creatine phosphokinase (CPK) and lactate dehydrogenase (LDH).

Fractionate bilirubin, if total bilirubin 2xULN

Obtain complete blood count with differential to assess eosinophilia

Record the appearance or worsening of clinical symptoms of liver injury, or hypersensitivity, on the AE report form

Record use of concomitant medications including acetaminophen, herbal remedies, other over the counter medications

Record alcohol use

For bilirubin or INR criteria:

Anti-nuclear antibody, anti-smooth muscle antibody, Type 1 anti-liver kidney microsomal antibodies, and quantitative total immunoglobulin G (IgG or gamma globulins)

Serum acetaminophen adduct HPLC assay (quantifies potential acetaminophen contribution to liver injury in subjects with definite or likely acetaminophen use in the preceding week [James, 2009])

Liver imaging (ultrasound, magnetic resonance, or computerized tomography) and /or liver biopsy to evaluate liver disease

Increased Monitoring Criteria with Continued Therapy

Criteria

 If ALT ≥5xULN and <8xULN and bilirubin <2xULN without symptoms believed to be related to liver injury or hypersensitivity, and who can be monitored weekly for 2 weeks

OR

 ALT ≥3xULN and <5xULN and bilirubin <2xULN without symptoms believed to be related to liver injury or hypersensitivity, and who can be monitored weekly for 4 weeks

Required Actions

- Notify GSK within 24 hours of learning of the abnormality to discuss subject safety
- Subject can continue study treatment
- Subject must return weekly for repeat liver chemistries (ALT, AST, alkaline phosphatase, bilirubin) until they resolve, stabilise or return to within baseline
- If at any time a subject meets the liver chemistry stopping criteria, proceed as described above for Required Actions and Follow up Assessments following ANY Liver Stopping Event
- If ALT decreases from ALT ≥5xULN and <8xULN to ≥3xULN but <5xULN, continue to monitor liver chemistries weekly

If, after 4 weeks of monitoring, ALT <3xULN and bilirubin <2xULN, monitor subjects twice monthly until liver chemistries normalize or return to within baseline.

Study-wide stopping rules: A study-wide stopping rule will be based on the comparison of serious adverse events rates between the two treatment groups. This safety endpoint will be

used instead of the primary endpoint since the primary endpoint is not a clinical marker of efficacy. The DSMB and sponsor (GSK) will have responsibility for invoking a study-wide stopping rule based on their evaluations of the data.

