measures seemed to be inversely concordant with interval changes of patient's clinical status (e.g., anti-GRP78 OD tended to increase as their lung disease severity got worse).

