2.8 DATA AND POWER ANALYSES

2.8.1 Primary Endpoint Data Analyses:

Baseline demographic and clinical data of participants will be summarized using means (with standard deviations) and medians (with inter-quartile ranges) for continuous variables, and counts and percentages for discrete variables, stratified by treatment group. Differences among groups (to examine the randomization effectiveness), will be assessed by t-tests, or by Fisher's exact test for discrete data, recognizing the limited power of our small trial.

Repeated measures linear mixed models will be used to evaluate differences of immunological parameters (continuous variables) that comprise the primary, and most second endpoints. These models will track the changes over time as well as allow for missing observations, which should be minimal. In general, analyses will follow intention to treat principles, with the last observed outcome over all time points being used as the primary measure for a given variable.

The sample size of 18 subjects for this clinical trial is based on exposing a minimum number of patients to potential risks of the experimental therapy, while having the potential to obtain useful information. Given that this trial is unprecedented, it is impossible to use preliminary data to definitively derive power analyses. Indeed, an important purpose of this study is to generate credible and relevant preliminary data in this population to power subsequent larger trials. Trials to detect clinical efficacy (e.g., change in pulmonary function tests, reductions in acute exacerbations, etc.) will almost certainly require treatment of many subjects over prolonged periods.

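### Two stopping rules in 5.6.4 end study participation, not just study drug, and 2.8.1 then lets an early anti-GRP78 value stand in for the month 7 result in the primary comparison

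*Combined protocol and SAP*

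**What the plan says.** The individual stopping rules in 5.6.4 open as rules about treatment: "A study participant will be discontinued from further study drug treatment/Intervention(s) administration if any of the following occur". The liver criteria in the same section keep to that: "The study treatment will be Immediately discontinued", with the subject monitored afterwards. Two items go further. For exacerbations: "Patients who develop acute exacerbations that require an addition to their lung medications, or a hospitalization, will be terminated from the study". For new exclusion statuses: "Any subject who develops new conditions or statuses that would have been an exclusion criterion, will be terminated from the trial".

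After removal, sections 2.6 and 5.6.2 provide for follow-up of the adverse event. Neither Table 2 nor 2.6.4 contains an early-termination or post-withdrawal immunologic sample. Section 2.9.1 counts exacerbation cases as drop-outs.

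On analysis, 2.8.1 states: "Repeated measures linear mixed models will be used to evaluate differences of immunological parameters", covering the primary endpoint, and adds that these models allow for missing observations. The population is then described: "In general, analyses will follow intention to treat principles". The rest of that sentence says which value represents each subject: "with the last observed outcome over all time points being used as the primary measure for a given variable". No contrast or time point is named for the model. Section 2.8.1 expects the reduction by or after roughly six months of treatment. Multiple imputation, to examine the problems of carrying observations forward, appears only in 2.8.2, for the secondary endpoints.

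**The concern.** Under these rules sampling of the primary endpoint stops at a clinical event, while the comparison is described as intention to treat. What happens to such a subject in the analysis depends on which of the two statements in 2.8.1 governs.

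- If the last observed value governs, a month 1 or month 3 measurement is compared with month 7 measurements in other subjects. Before month 6 it measures a different quantity.
- If the mixed model governs, the early value is used properly as an early value. The month 7 difference then rests on the data being missing at random, which the observed data cannot test.

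That assumption is open to some doubt. Section 2.7.1 reports from serial specimens that "anti-GRP78 OD tended to increase as their lung disease severity got worse". If an exacerbation marks worsening disease, the event that ends sampling may be related to the endpoint. The trial is meant to supply preliminary data for powering later trials, so a distorted effect estimate would carry forward.

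**Working it through.** **Inputs from the plan (2.8.1):** difference 30 points, SD 20, 12 belimumab and 6 placebo, Type I error 0.05. Samples at months 1, 3, 5 and 7 (2.7.1). The synopsis randomizes 25 to reach 18.

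**Assumptions, not in the plan:** placebo mean change 0; effect builds linearly to month 6, so the fraction present is 1/6 at month 1, 1/2 at month 3 and 5/6 at month 5; the 25 split 17/8; exactly one subject affected.

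**Plan's own figure.** Standard error = 20 × √(1/12 + 1/6) = 10. Non-centrality = 30/10 = 3.0 on 16 degrees of freedom. Two-sided t-test power is 0.804, so the stated 0.8 is reproduced. For 17/8 the standard error is about 8.6 and power 0.918.

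**If the last observed value decides, with the full effect otherwise kept.** Expected difference on 12/6 = 30 × (11 + f)/12, where f is the fraction present at the last sample. Power is from a simulated t-test.

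| Last sample | f | Expected difference, 12/6 | Loss | Power 12/6 | Power 17/8 |
|---|---|---|---|---|---|
| Month 1 | 1/6 | 27.92 | 2.08 | 0.716 | 0.878 |
| Month 3 | 1/2 | 28.75 | 1.25 | 0.760 | 0.898 |
| Month 5 | 5/6 | 29.58 | 0.42 | 0.792 | 0.911 |

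**If the mixed model decides and data are missing at random.** The expected difference stays 30. If the subject added nothing at month 7, power would be that of 11/6, which is 0.789, or of 16/8, which is 0.911. A small simulation of the model (simulation error about 0.02) gave 0.80 to 0.81 on 12/6 and 0.92 on 17/8.

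**Sensitivity to the unseen month 7 value.** Let r be the fraction of the effect that the terminated belimumab subject would truly have at month 7. True difference = 30 × (11 + r)/12. The last sample is at month 1, so the last-value estimate is 27.92; the mixed model gives 30.

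| r | True difference | Error, last value | Error, mixed model |
|---|---|---|---|
| 1 | 30 | -2.08 | 0 |
| 0.5 | 28.75 | -0.83 | +1.25 |
| 0 | 27.5 | +0.42 | +2.5 |
| -0.5 (a 15-point rise) | 26.25 | +1.67 | +3.75 |

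If one of six placebo subjects is terminated before a 15-point rise, both methods are off by -15/6 = -2.5. On 17/8 the extremes shrink to -15/8 = -1.9 and +2.65.

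**Cost in power of sampling after drug stop.** With one of 12 off drug on 12/6, simulated power is 0.76 if half the effect is kept and 0.69 if none.

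**The case against.** The opposing case has real weight.

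- **Size.** The largest error from one subject, 3.75 points, is under 0.4 standard errors in a trial that presents itself as proof of concept with limited power. A reader might infer that one subject shifts the result by up to 4 points either way. The figures do not support that: downward errors stop at 2.5, several scenarios give less than 2, and the extremes in both directions rest on a 15-point rise that has no source in the documents.
- **Link to the endpoint.** A reader might also infer that exacerbations raise anti-GRP78. The observation in 2.7.1 concerns specimens taken two years apart, which correlated above 0.82. It says nothing direct about an acute event within seven months.
- **Frequency.** No termination rate is given, recent exacerbators are excluded, and 2.9.1 expects retention near 100%. The seven extra subjects among 25 cannot be read as an exacerbation rate, because the synopsis attributes early withdrawals to COVID-19 and to medical reasons unrelated to drug or procedures.
- **Target.** The errors above are measured against a month 7 difference that includes time off drug. For a small pharmacodynamic pilot the on-drug effect is also a defensible target, and continued sampling then dilutes it. An exacerbation may also bring oral steroids, themselves an exclusion, which could affect later values. The protocol does not give this as the reason for the rule.
- **Clarity of 2.8.1.** The primary-measure wording can be read as settling the matter in favor of the last observed value.

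These points limit the size of the concern and make continued sampling a matter of judgment. They do not remove the main problem. If the last observed value does decide, early values enter the primary comparison by design, and the plan's own check for this does not cover the primary endpoint.

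**Conclusion.** The concern holds in a limited form. The two rules terminate participation. That no later anti-GRP78 samples are planned is an inference from the absence of any such provision, and no text contradicts it. The primary analysis can then use a month 1 or month 3 value where a value at about six months is meant.

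With the full effect otherwise kept, one belimumab subject carried from month 1 costs 2.1 points and takes power from 0.804 to 0.72 on 12/6, or from 0.918 to 0.88 on the assumed 17/8. Later last samples cost much less. Across the scenarios tried, one subject's error on 12/6 runs from about -2.5 to +3.75 points. These figures depend on the linear build-up, the assumed unseen values and the choice of target. The documents do not establish how many subjects are affected, which way any bias runs, or that it favors belimumab. The plan should be changed mainly because naming a better deciding analysis costs nothing.

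**What to change.** **(a) Section 2.8.1.** State that the deciding analysis is the mixed model on all randomized subjects in their assigned arm, with the arm difference at month 7 as the main contrast. Make the last observed value a sensitivity analysis. Apply the multiple-imputation check of 2.8.2 to the primary endpoint. This also settles whether 18 or all 25 subjects are analyzed. It costs only wording and helps even if nobody is terminated.

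**(b) Section 5.6.4.** Let the two triggers stop study drug only, with no change to when drug stops. Keep the remaining scheduled immunologic samples (days 30, 90, 150, 210) and the month 8 and 10 contacts, unless consent is withdrawn or the investigator judges a draw unsafe. Add an on-treatment sensitivity analysis that leaves out values after drug stop or after the start of an oral steroid. Section 2.6.4 already records concomitant medications at each time point.

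The cost of (b) is at most four 29 ml draws and two contacts per stopped subject, all at times already scheduled, plus the possible dilution shown above. The gain is less reliance on an untestable assumption, not more power. It reaches only subjects still to be stopped; for those already withdrawn, existing samples are used.
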